### 11.1 STATISTICAL ANALYSIS STRATEGIES

The statistical analysis plan below aligns with the aims that are described in Section 2.3. all statistical estimates of population parameters will be tabulated along with corresponding confidence intervals (CIs) to convey levels of precision / imprecision. All hypothesis tests that yield large p-values ( $p>0.05$ ) will be reported as being inconclusive.

*Phase One* overarching goal: Investigate the causal role of frontal theta and parietal alpha oscillations in the prioritization and suppression of working memory representations. To control for non-specific effects of rhythmic TMS, we will use an active control: arrhythmic TMS (randomized inter-pulse-interval) that is matched to the target stimulation in number of pulses and temporal duration. All analyses will be performed on the difference from condition-matched arrhythmic TMS. The key analyses are built upon a three-way parallel arms design: with factors TMS frequency (theta versus alpha), location (frontal versus parietal), and cue direction (left versus right retro-cue). There is an equal number of trials for each of these conditions and there are 75 trials for each condition per participant.

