forms of arrhythmic stimulation are used: arrhythmic-in-synchrony stimulation delivers simultaneous stimulation to the two sites, but there is no consistent frequency component to the stimulation. Thus, activity in the two sites may be synchronized but not in a frequency-specific manner. The second control condition for stimulation is arrhythmic-independent where two trains of TMS are delivered in random patterns. There is no synchronization between the two pulse trains. Arrhythmic-independent controls for frequency and synchrony specificity of stimulation. All analyses will be performed on the difference from condition-matched arrhythmic TMS (in-phase minus arrhythmic-in-synchrony and anti-phase minus arrhythmic-independent). The key analyses are built upon a three-way design: with factors TMS frequency (theta and alpha), TMS alignment (in-phase and anti-phase), and cue direction (left and right retro-cue).

**Aim 6 (primary outcome):** Stimulation that is delivered in-phase to frontal and parietal cortex in the theta frequency is hypothesized to increased working memory capacity relative to anti-phase theta stimulation. Working memory capacity is quantified using Pashler's metric (see Aim 1). We will perform a two-way repeated-measures ANOVA with a between participants factor of TMS frequency (theta and alpha) and within-participants factor of TMS alignment (in-phase and anti-phase). We hypothesize to find a significant interaction ( $p < 0.05$ ) between TMS frequency and TMS alignment such that in-phase TMS in theta-frequency increases working memory capacity. Post-hoc t-tests will be performed using Tukey's method to control for multiple comparisons. *Sensitivity analysis:* Similar to aim 1, the impact of stimulation on hit rate, false alarm rate, and overall accuracy will be calculated. The robustness of these effects will be estimated using an individual differences analyses where baseline performance is used as a covariate to improve model estimation. Finally, the titration of working memory load by participant will be added as a covariate to explore if this factor changes the model estimation. These are framed as exploratory analyses.

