
of our a priori effect. Furthermore, these confirmatory sensitivity analyses avoid the multiple comparisons problem by relying on the initially established analyses.

**Aim 8 (secondary outcome):** Stimulation that is delivered in-phase is hypothesized to decrease the relative phase difference (phase lag) between the frontal and parietal cortex, whereas anti-phase stimulation is hypothesized to increase the phase lag. If stimulation entrained neural activity directly to the stimulation train, then this pattern of phase lag differences would be expected (because in-phase stimulation is delivered with zero phase lag and anti-phase stimulation is delivered with a phase lag). To calculate phase lag, first Morlet wavelet convolution is performed to extract instantaneous phase and amplitude for the frequency of interest for the two target sites. Next, the cross-spectral density is calculated (one signal multiplied by the complex conjugate of the other). From the cross-spectral density the phase angle is extracted, this is the phase lag. Then those phase lag values are averaged over the time frame of instance (here, the second half of the stimulation train). Finally, the angle of the resulting vector is taken to be the average phase lag. This metric quantifies the degrees of phase lag between the two target regions. Using a two-way ANOVA with factors for TMS frequency (theta or alpha) and TMS alignment (in-phase or anti-phase), we hypothesize a significant main effect ( $p < 0.05$ ) of TMS alignment such that phase lag is different between in-phase and anti-phase where in-phase decreases the phase lag and anti-phase increases the phase lag. We also hypothesize that this effect will be strongest for theta-frequency stimulation, which is hypothesized to be revealed as a significant main effect between TMS frequency and TMS alignment. Post-hoc t-tests will be performed using Tukey's method to control for multiple comparisons. *Sensitivity analysis:* Similar to Aim 7, the spread of stimulation effects in time, space, and frequency will be explored.

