## 11.2 SAMPLE SIZE RATIONALE

Based on a previous study with the current behavioral paradigm and similar TMS manipulation, the effect size of the interaction between TMS site and TMS frequency on WM capacity was 0.532 and used 21 participants. A power analysis of this effect suggests that to reach 95% statistical power we would need to recruit 48 participants. Therefore, we will perform our final analysis on 48 participants. Previous studies using a similar methodology of concurrent rhythmic TMS and EEG to look for changes in oscillatory power of the frequency of rhythmic TMS have used 10 participants for alpha frequency TMS (Thut et al., 2011) and 17 participants for theta rhythmic TMS (Albouy et al. 2017). Here, we propose to collect 48 participants. Therefore, our statistical power exceeds that of previous studies published in high-impact journals using a nearly identical methodology. Furthermore, we utilize a repeated-measures inter-mixed design in order to maximize our ability to control for confounding variables and increase statistical power. Based on a previous study by Thut et al., 2011 that found an increase in alpha oscillatory power from alpha rhythmic TMS relative to arrhythmic TMS with an effect size of 0.83 and 10 participants, we would need 21 participants to reach 95% statistical power for this comparison. Based on a previous study by Albouy et al., 2017 that found an increase in theta oscillatory power from theta rhythmic TMS relative to arrhythmic TMS with an effect size of 0.56 and 17 participants, we would need 44 participants to reach 95% statistical power for this comparison. Therefore, we estimate that based on these previously reported effect sizes for the impact of rhythmic TMS on behavior and oscillatory power measured by EEG in similar studies and our proposed sample size of 48 participants, we conclude that the proposed study has sufficient statistical power to answer the posed hypotheses.

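### Aim 8 names a main effect as the evidence that the alignment effect is strongest for theta; only the frequency-by-alignment interaction tests that

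*Combined protocol and SAP*

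**What the plan says.** Section 11.1, Aim 8 sets out the model: "Using a two-way ANOVA with factors for TMS frequency (theta or alpha) and TMS alignment (in-phase or anti-phase"). It then makes two predictions.

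- The first is that alignment matters: "we hypothesize a significant main effect ( $p < 0.05$ ) of TMS alignment such that phase lag is different between in-phase and anti-phase".
- The second is that this effect is strongest under theta stimulation, "which is hypothesized to be revealed as a significant main effect between TMS frequency and TMS alignment".

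Post-hoc comparisons follow: "Post-hoc t-tests will be performed using Tukey's method to control for multiple comparisons". The aim does not say which contrasts they cover.

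Aim 6 has the same two factors, with frequency between participants and alignment within. There the plan predicts a significant interaction "between TMS frequency and TMS alignment such that in-phase TMS in theta-frequency increases working memory capacity". Aim 7 also ties its theta-specific prediction to an interaction.

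The statement of Aim 8 in Section 2.3 covers only in-phase versus anti-phase phase lag. It has no theta claim and no test, so the sentence in Section 11.1 is the only place where the theta criterion is written.

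**The concern.** The second prediction compares two differences: in-phase minus anti-phase under theta, against the same quantity under alpha. Its null hypothesis is that the two are equal, and in a two-way ANOVA that is the interaction null. The alignment main effect has another null, that the average difference over both arms is zero. It can be rejected when theta and alpha respond equally, or when only alpha responds. The frequency main effect compares overall phase lag between arms and says nothing about alignment.

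Section 2.2 includes alpha stimulation as the control for frequency specificity, and the background in Section 2.1 expects alpha connectivity to be inconsequential. Aim 8's second prediction carries that idea over to phase lag. If its criterion is worded as a main effect, an analyst or reader could take the alignment result as support for theta specificity when it is not evidence for it.

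**Working it through.** **Inputs**

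- Phase two has 48 completers (Section 3).
- Each phase two participant receives either theta or alpha in both stimulation sessions (Section 4.1), so frequency is a between-participant factor, as Aim 6 says. The ratio is not stated; 24:24 is assumed.
- The significance threshold is 0.05: "All hypothesis tests that yield large p-values ( $p>0.05$ ) will be reported as being inconclusive". Sidedness is not stated.
- No effect size is given for phase lag. The nearest figure is in Section 11.2: "the effect size of the interaction between TMS site and TMS frequency on WM capacity was 0.532 and used 21 participants".

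**The plan's own figure first.** For a paired t-test, power comes from the noncentral t with n − 1 df and noncentrality d√n. With d = 0.532 and n = 48, noncentrality is 0.532 × 6.928 = 3.686, and two-sided 0.05 gives power 0.9505. The smallest n reaching 95% is 48, as stated. The same formula returns the plan's 21 (d = 0.83) and 44 (d = 0.56). A one-sided test would give 40 instead of 48, so two-sided 0.05 is used below. This figure is for working memory capacity, not for Aim 8.

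**The two tests in Aim 8.** Let D be each participant's in-phase minus anti-phase phase lag, in units of its own SD, with mean δθ in the theta arm and δα in the alpha arm. With 24 per arm and 46 df:

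- Alignment main effect: noncentrality = [(δθ + δα)/2] × √48
- Interaction: noncentrality = (δθ − δα) × √(24/2) = (δθ − δα) × √12

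| δθ, δα | Main effect noncentrality | Main effect significant | Interaction noncentrality | Interaction significant |
|---|---|---|---|---|
| 0.3, 0.3 | 2.08 | 53% | 0 | 5% |
| 0.5, 0.5 | 3.46 | 92% | 0 | 5% |
| 0.532, 0.532 | 3.69 | 95% | 0 | 5% |
| 0.8, 0.8 | 5.54 | over 99.9% | 0 | 5% |
| 0, 0.8 | 2.77 | 77% | −2.77 | 77%, opposite direction to the claim |
| 0.532, 0 | 1.84 | 44% | 1.84 | 44% |

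Simulation of the same design agrees within simulation error.

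In the first four rows the theta-specific claim is false. The main-effect column there is simply its power to detect an alignment effect that exists. It becomes a false-claim rate only if theta specificity is read from that test.

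**If the frequency main effect were meant.** With equal alignment effects of 0.532 SD and no overall frequency difference, it is significant in about 5% of simulated trials. With a theta-only alignment effect placed symmetrically around the arm mean, it is also significant about 5% of the time. It does not inflate the false-claim rate in that setting, but it does not detect the claimed pattern either.

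**Do the post-hoc tests settle it?** Not clearly. A result significant in theta but not in alpha is not a test of the difference. With a true effect of 0.5 SD in both arms, an unadjusted within-arm test on 24 participants has power 0.650, so that pattern arises with probability 0.650 × 0.350 = 0.23.

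**Cost in power of the right test.** For a theta-only effect of 0.532 SD, interaction power with 24 per arm is about 44%. Reaching 95% would take about 93 per arm.

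**The case against.** The strongest reply is that this is a one-word slip. A main effect does not lie between two factors; an interaction does. Aim 6 uses the same construction correctly, and Aims 1 to 5 and 7 also pair interaction with two named factors. Aim 8 already lists the alignment main effect as a separate hypothesis, so its second criterion, which adds frequency, cannot sensibly be the first one repeated. The specified ANOVA produces the interaction anyway. The direction is stated, and estimates are to be tabulated with confidence intervals, so an alpha-only result would be visible. Aim 8 is secondary, and frequency specificity is tested in the primary Aims 6 and 7, which name an interaction.

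Most of this stands. A reader might infer that the plan would report an equal effect in both arms as theta-specific, or that the theta claim has no test of its own. The documents support neither. No section says that an alignment main effect will be reported as theta-specific, and the sentence names both factors.

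The reply does not remove the error. The sentence is the only prespecified criterion for the claim, and the test it names is wrong as written. Low interaction power adds to the problem: a non-significant interaction is likely even if the claim is true, and an ambiguous criterion is then easy to reinterpret once results are known.

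**Conclusion.** The point holds as a wording error in an inferential criterion of a secondary aim. The claim that alignment matters most for theta is the frequency-by-alignment interaction, and Aim 8 calls it a main effect. The likely intention is the interaction.

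The consequence is conditional. Only if the sentence is taken to mean the alignment main effect could an equal effect in both arms pass as theta-specific, about 53% of the time at 0.3 SD and 92% at 0.5 SD, against 5% for the interaction. These are not error rates of the plan as most readers would understand it. They assume a 24:24 split, equal variances, a two-sided 0.05 level, illustrative effect sizes, and phase lag treated as a linear rather than circular quantity. Aims 6 and 7 are unaffected.

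**What to change.** In Section 11.1, Aim 8, replace main effect with interaction in the sentence on theta. Add that theta specificity will be claimed only if the TMS frequency by TMS alignment interaction is significant (p<0.05) with the larger alignment difference in the theta group. Keep the alignment main effect as the criterion for the first hypothesis only.

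The cost is one or two sentences. The model is the same and no further data are needed. The downside is power: the interaction is a between-group comparison, with about 44% power for a theta-only effect of 0.532 SD at 24 per arm. It would help to say so in the plan, so that a non-significant interaction is read as inconclusive, as Section 11.1 already provides.

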## 11.2 SAMPLE SIZE RATIONALE

Based on a previous study with the current behavioral paradigm and similar TMS manipulation, the effect size of the interaction between TMS site and TMS frequency on WM capacity was 0.532 and used 21 participants. A power analysis of this effect suggests that to reach 95% statistical power we would need to recruit 48 participants. Therefore, we will perform our final analysis on 48 participants. Previous studies using a similar methodology of concurrent rhythmic TMS and EEG to look for changes in oscillatory power of the frequency of rhythmic TMS have used 10 participants for alpha frequency TMS (Thut et al., 2011) and 17 participants for theta rhythmic TMS (Albouy et al. 2017). Here, we propose to collect 48 participants. Therefore, our statistical power exceeds that of previous studies published in high-impact journals using a nearly identical methodology. Furthermore, we utilize a repeated-measures inter-mixed design in order to maximize our ability to control for confounding variables and increase statistical power. Based on a previous study by Thut et al., 2011 that found an increase in alpha oscillatory power from alpha rhythmic TMS relative to arrhythmic TMS with an effect size of 0.83 and 10 participants, we would need 21 participants to reach 95% statistical power for this comparison. Based on a previous study by Albouy et al., 2017 that found an increase in theta oscillatory power from theta rhythmic TMS relative to arrhythmic TMS with an effect size of 0.56 and 17 participants, we would need 44 participants to reach 95% statistical power for this comparison. Therefore, we estimate that based on these previously reported effect sizes for the impact of rhythmic TMS on behavior and oscillatory power measured by EEG in similar studies and our proposed sample size of 48 participants, we conclude that the proposed study has sufficient statistical power to answer the posed hypotheses.

It should be noted that our experimental design improves upon previous designs by sufficiently powering our “small  $n$ ,” of the number of trials per condition (Nee 2019). This factor is often overlooked in many power analyses. For the proposed experimental design, 75 trials per condition ensures that we have sufficient power at the level of each participant. The number of trials is critical to increasing the precision of each estimated metric for each participant. Some analyses of statistical power have found that this aspect is sometimes more important than the number of

participants. We maximize our statistical power by using a large number of trials for each participant and by using a large number of participants, relative to standard sample and trial sizes in the literature.

### 11.3 DATA MANAGEMENT

Data will be stored in a password-protected cloud-based data system that does not contain any participant information. Individual records are referred to by dummy identifiers that cannot be traced back to the study participants except with the master code list that is stored separately in a secured location.

Information about study participants will be kept confidential and managed according to the requirements of the Health Insurance Portability and Accountability Act of 1996 (HIPAA). Those regulations require a signed participant authorization informing the participant of the following:

- What protected health information (PHI) will be collected from the participants in this study
- Who will have access to that information and why
- Who will use or disclose that information

-The rights of a research participant to revoke their authorization for use of their PHI.

In the event that a participant revokes authorization to collect or use PHI, the investigator, by regulation, retains the ability to use all information collected prior to the revocation of participant authorization. For participants that have revoked authorization to collect or use PHI, attempts should be made to obtain permission to collect at least vital status (i.e., that the participant is alive) at the end of their scheduled study period.

The responsibilities designated to each member of the research team are documented on the Delegation of Authority Form. The researcher will be responsible for the informed consent process, review for eligibility, questionnaire administration, data entry, device administration, EEG administration, and CRF entries. The researcher will be responsible for AE/SAE documentation and reporting, while the PI will be responsible for the AE assessment, review of the AE documentation forms, and overview of the research staff.

All data (including AEs, concomitant medications, and expected adverse reactions data) will be entered into a data capture system provided by REDCap. The data system includes password protection and internal quality checks, such as automatic range checks, to identify data that appear inconsistent, incomplete, or inaccurate. Clinical data will be entered directly from the source documents.

All assessments completed by the participant at home will be completed via REDCap as well, ensuring participant security and confidentiality.

All deviations from the protocol will be addressed in study participant source documents. The researcher will complete a Protocol Deviation Log using the participant code as the identifier. This form will collect information such as the date the deviation occurred, details of what the deviation consisted of, any corrective and preventative actions that were taken as a result of the deviation, and the date that the PI and IRB were notified. The PI will review the information and initial once approved. A completed copy of the Protocol Deviation Form will be maintained in the regulatory file, as well as in the participant's source document. Protocol deviations will be sent to the IRB per their guidelines. The site PI/study staff will be responsible for knowing and adhering to their IRB requirements.

According to the University of North Carolina at Chapel Hill's Archives and Record Management Services schedule for General Records Retention and Disposition Schedule 6.10, records will be kept for 5 years after the completion of the study or grant end date, whichever is later.

## 12 DATA HANDLING AND RECORD KEEPING

The researchers are responsible for the accuracy, completeness, legibility, and timeliness of the data reported.

### 12.1 PHI AND HIPAA

Information about study participants will be kept confidential and managed according to the requirements of the Health Insurance Portability and Accountability Act of 1996 (HIPAA). Those regulations require a signed participant authorization informing the participant of the following:

- What protected health information (PHI) will be collected from the participants in this study
- Who will have access to that information and why
- Who will use or disclose that information
- The rights of a research participant to revoke their authorization for use of their PHI.

In the event that a participant revokes authorization to collect or use PHI, the investigator, by regulation, retains the ability to use all information collected prior to the revocation of participant authorization. For participants that have revoked authorization to collect or use PHI, attempts should be made to obtain permission to collect at least vital status (i.e., that the participant is alive) at the end of their scheduled study period.

### 12.2 CONFIDENTIALITY

#### 12.2.1 ACCESS TO SOURCE DOCUMENTS

The researchers and PI will have access to all of the source documents collected over the course of the study. The medical monitor will have access to files upon request, as they will need access to the locked filing cabinets and rooms in which these documents are located.

Data will stay on a password-protected computer. Subsequently, a copy will be processed on a separate, password-protected desktop computer in the [name] Lab ([name]).

#### 12.2.3 OTHER

Please note that there is no significant risk of deductive disclosure in this study. In addition, none of the groupings or subgroupings used in analysis will be small enough to allow individuals to be identified.

